Précis	A total of 700 subjects will be enrolled. To measure the incidence of contrast-induced nephropathy (CIN), subjects (n = 600) with suspected pulmonary embolism (PE) will be prospectively randomized to CT of the pulmonary arteries (CTPA, iodinated contrast media exposure) or to ventilation-perfusion scintigraphy (VQ, unexposed control). To validate a risk-stratification tool for AKI, alone and in combination with acute-phase markers of renal dysfunction (Cystatin-C and NGAL) in both the exposure and unexposed controls, as well as, an additional non-randomized 100 subjects who will undergo CTPA for suspected PE. All subjects will be followed for the development of acute kidney injury (AKI) occurring ≥ 48 hours and ≤ 168 hours following imaging and subsequent long-term outcomes.
Primary Study Objective	Compare the incidence of acute kidney injury (AKI) consistent with contrast-induced nephropathy (CIN) in 600 patients with suspected PE and an AKIrisk Score ≥ 2 , randomized to CTPA (contrast media exposure) or VQ (unexposed control) imaging.
Secondary Study Objectives	
 1) Validate the AKIRisk score, alone and in combination with acute-phase markers of renal dysfunction (Cystatin-C and/or NGAL), to inform imaging strategies and reduce the risk of CIN. 2) Compare the incidence of AKI and subsequent severe health outcomes in patients exposed to iodinated contrast media and unexposed controls at 30-days and 1-year. 3) Measure the 30-day and 1-year incidence of VTE and subsequent severe health outcomes including outcomes related to VTE and VTE treatment
Safety Objectives	Compare the safety outcomes in both the CTPA and VQ groups including outcomes associated with imaging type, VTE (diagnosed and missed), and treatment of VTE occurring within 7 days of enrollment study imaging.
Primary Endpoint	AKI consistent with CIN, defined as an increase in creatinine $\geq 25\%$ of baseline or an absolute increase in creatinine to ≥ 0.5 mg/dL ≥ 48 hours and ≤ 168 hours of the enrollment PE imaging study.
Safety Endpoints	
Defined as one or more of the following events occurring within 7 days (168 hours) of the enrollment PE imaging study:
 
 1) Time to treatment of PE > 8 hours defined as the time from study enrollment until initiation of anticoagulant therapy for PE. 2) Complications of PE imaging defined as one or more of the following occurring within 24 hours of the enrollment imaging study and requiring medical or surgical intervention: hypotension, difficulty breathing, acute pulmonary edema or hypervolemia, oral swelling, rash or puritis, abdominal pain, nausea or vomiting, altered mental status, or soft tissue contrast media or radio-isotope extravasation.

	
3) Severe health outcomes defined as one or more of the following occurring within 168 hours of the enrollment imaging study: AKI (Acute Kidney Injury Network [AKIN] 1-3); Death (any cause), renal failure, or one or more of the following requiring medical or surgical intervention: acute myocardial infarction, stroke and/or other acute arterial vascular event, in any anatomic distribution, requiring medical or surgical intervention; death with renal injury as a significant contributor defined as obvious evidence of renal failure defined by worsening azotemia with complications of renal failure including oliguria, pulmonary edema, hyperkalemia, pericardial effusion, or the need to initiate renal replacement therapy before death; identification of a venous thromboembolism (VTE, PE and/or DVT) requiring medical or surgical intervention; death from VTE and/or hemorrhage requiring medical or surgical intervention as a result of treatment for VTE.

Tertiary End-points	Mid- (occurring within 30 days) and Long-term (occurring within 1 year) severe health outcomes
Number of Subjects	
 • A total of 700 subjects will be enrolled inclusive of 600 subjects that will be randomized to CTPA or VQ imaging and 100 non-randomized subjects that will undergo CTPA.
Inclusion Criteria	
 1) Age ≥ 18 years CTPA ordered by the treating provider to evaluate PE. 2) Pre-test probability of PE $\leq 20\%$ defined using the PE Pretest Consult Score. 3) For randomization to CTPA or VQ imaging (600 subjects): AKI risk $\geq 20\%$ assessed by an AKIrisk Score ≥ 2 points 1) For non-randomized CTPA group (100 subjects): AKI risk $< 10\%$ assessed by an AKIrisk Score < 2 points.
Exclusion Criteria	
 1) A history of pulmonary surgery. 2) Findings on chest-radiograph that may limit the accuracy of VQ imaging for the detection of PE including air-space disease occupying more than 50% of the lung field, significant mass, or pleural effusion of significant volume or associated with low-lobe air-space disease. 3) Clinical instability or other condition preventing randomization to CTPA or VQ imaging as reported by the treating provider. 4) Pregnancy or ≤ 48 hours post-partum. 5) Subject unavailability for reasonable follow-up including biological sample collection, creatinine measurement, and interview, such as an insecure residence, planned travel or absence, personal or professional obligations, incarceration, and/or other reason preventing follow-up, identified at enrollment. 6) Active renal replacement therapy (hemodialysis or peritoneal dialysis) within 30-days of enrollment or previous physician-directed plans to initiate dialysis within 30-days of the index visit. 7) Prior renal transplant or planned within 30-days of enrollment.

	Intravascular iodinated contrast media administration within 14 days prior to enrollment or planned within 7 days of enrollment.
Population characteristics	We expect approximately 60% women and 35-50% minority representation, and 1-3% of Hispanic/Latino origin.
Study Sites	We will enroll patients at 5 sites. IUH Methodist Hospital (also provides emergency care to IUH University Hospital), Eskenazi Hospital, IUH Ball Memorial Hospital, University of Utah, and Intermountain Healthcare
Description of Study Intervention	Subjects will undergo 1 of 2 standard of care diagnostic imaging studies for suspected pulmonary embolism. Study Inclusion and Exclusion Criteria specifically select patients that are appropriate for evaluation by either imaging study.
Study Duration	Study enrollment and follow-up for primary and outcome measures will be completed within 4 years. Subject participation will last for 1 year.

Key Personnel

Principal Investigator

[name], MS
Indiana University School of Medicine
[name]
[name]
[contact]
Email: [contact]

Co-Investigator

[name]
Indiana University School of Medicine
[name]
[name]
[contact]
Email: [contact]

Co-Investigator

[name]
Indiana University School of Medicine
[name]
[name]
[contact]
Email: [contact]

Co-Investigator

1.1 Study Overview

Despite widespread use of less nephrotoxic, contemporary iodinated contrast media agents, contrast-induced nephropathy (CIN) remains a leading cause of acute kidney injury (AKI), occurring as frequently now as in the 1970s.¹ Human exposure to iodinated contrast media agents is now a large and rapidly growing public health problem: over 40 million patients are exposed annually with CT imaging studies.² The rate of CT imaging has increased exponentially over the past decade, and >25% of exposures now occur in the emergency care setting.^{3,4} Patients evaluated for pulmonary embolism (PE) are among the mostly likely to be exposed: >10% of the patients evaluated for chest symptoms in the emergency care setting undergo contrast-enhanced CT of the pulmonary arteries (CTPA).⁵ Less than 1% of these patients, and only who physicians considered to be at the most extreme risk of CIN, undergo non-contrast imaging for PE, namely ventilation-perfusion scintigraphy (VQ).⁴⁻⁶

Preliminary work demonstrates the following:

- 1) More than 15% of patients that undergo CTPA develop AKI consistent with CIN.⁷
- 2) An elevated creatinine (eGFR <60 ml/min/m²) has poor sensitivity (13%) for the prediction of CIN.⁸⁻¹⁰
- 3) Even after adjusting for age and co-morbidities, patients who develop CIN after contrast-enhanced CT have a 2-fold increased risk of death, renal failure and major cardiovascular events over the next year.¹¹

These findings motivated the applicant to derive a clinical prediction rule, the "AKIrisk Score:" age ≥50 years (1 point), HIV (1 point), coronary artery disease (1 point), diastolic hypertension ≥100 mmHg (1 point), and glycosuria ≥250 mg/dL (2 points). This score is a significant improvement over pre-CT creatinine screening: AUROC 0.75; AKIrisk Score ≥2 points with 60% sensitivity and predictive value positive of 27%.⁸ Preliminary data also demonstrate that acute-phase biomarkers of renal dysfunction, Cystatin-C and Neutrophil Gelatinase-Associated Lipocalin (NGAL), improve the predictive accuracy for CIN.^{9,10}

As a specialty, emergency physicians are particularly facile with the use of clinical decision rules.¹² In fact, clinical decision rules guiding the use of CTPA imaging are among the most well-known and widely adopted in emergency care practice.¹² However, current emergency medicine PE clinical decision rules do not consider CIN from CTPA imaging, resulting in both a lack of knowledge of the risk and subsequent outcomes of CIN, and the underuse of imaging strategies that prevent contrast media exposure.¹³

1.2 Study Hypothesis

The study hypothesis is that while a clinical decision rule more accurately risk-stratifies patients for AKI than creatinine screening, subsequent avoidance of exposure to contemporary contrast media agents does not alter overall AKI-risk. The alternative study hypothesis is that contrast media exposure is associated with an increased risk of AKI and the AKIrisk Score can be used to guide selective VQ imaging and reduce CIN in patients evaluated for PE in the emergency care setting.

This project will accomplish the following specific aims:

- 1) In 100 patients undergoing CTPA for suspected PE, test the accuracy of a AKIrisk Score <2 to predict a CIN-risk <10%.
- 2) Test if the use of acute-phase markers of renal dysfunction, Cystatin-C and/or NGAL, improves the predictive accuracy of the AKIrisk Score.
- 3) Compare the incidence of AKI consistent with CIN in 600 patients with suspected PE and a AKIrisk Score ≥2, randomized to standard CTPA (contrast media exposure) or VQ (unexposed control) imaging.

The outcomes of this research will 1) Validate effective methods of risk-stratifying patients for AKI-risk in the heterogeneous, real-world emergency care setting; and 2) Provide the rigorous evidence needed to change imaging practices and either a) more effectively prevent CIN OR b) Improve the utilization of imaging resources and avoid delays currently caused by unnecessary screening and prevention practices. These outcomes are central to future advances in AKI prevention in the emergency care setting and to optimizing current imaging practices; current time and resource consuming CIN-prevention methods characteristic of current clinical practice

will not change without prospective validation with a randomized, controlled trial.^{1, 3, 4} The specific translational impacts include 1) Quantification of the risk of AKI from contrast media exposure in the emergency care setting, 2) Validation of a clinical decision rule for the prediction of with either multi-cause AKI or CIN specifically, and 3) Vetting of two acute phase markers of renal dysfunction for use in the real-world, emergency care setting.

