We will reject the null hypothesis and the two groups, CTPA and VQ, will be considered equivalent if

$$\frac{\hat{P}_1 - \hat{P}_2 - \delta}{\sqrt{\hat{P}_1(1 - \hat{P}_1)/n_1 + \hat{P}_2(1 - \hat{P}_2)/n_2}} < -z_{0.05} \quad \text{and} \quad \frac{\hat{P}_1 - \hat{P}_2 + \delta}{\sqrt{\hat{P}_1(1 - \hat{P}_1)/n_1 + \hat{P}_2(1 - \hat{P}_2)/n_2}} > z_{0.05}$$

If we reject the hypothesis of equivalency, we will conduct an analysis for a superior trial. Hence, for comparison with the dichotomous primary outcome, that is, whether a subject develops AKI at the 2-7 day follow-up, a logistic regression model will be used. Group comparisons will be adjusted for baseline covariates. To validate the decision rule in classifying subjects into a low-risk group we will: 1) Measure the AKI rate in the low-risk group (AKIRisk Score <2) with a desired margin of error. We assumed the upper limit of the one-way 95% confidence interval to be <10%, based on preliminary data, and prior literature.^{6,7} as such, we will compute the one-way 95% confidence interval using a Z test statistic; and 2) Compute sensitivity and specificity of the decision rule.

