2.2 Secondary objectives

The secondary objectives of this study are to:

- 1) Validate the AKIRisk score, alone and in combination with acute-phase markers of renal dysfunction (Cystatin-C and/or NGAL), to inform imaging strategies and reduce the risk of AKI.
- 2) Compare the incidence of short, mid- and long-term AKI and subsequent health outcomes in patients exposed to iodinated contrast media and unexposed controls at 30-days and at 1-year.
- 3) Measure the 30-day and 1-year incidence of VTE and subsequent severe health outcomes including outcomes related to VTE and VTE treatment.

All secondary outcomes will be defined using composite outcomes and will be determined to be present or absent by the agreement of 2 of 3 blinded physician reviewers, using methods of adjudication successfully employed by the PI in comparable studies.^{7,11,20,46,53,59} Briefly, physician reviewers will be provided with copies of the EMR and patient interview responses. Identifying information will be redacted, and, while the reviewer will have access to any creatinine values recorded in the EMR, they will not be provided with creatinine measurements performed for the study and not recorded in the EMR, nor will they be informed of the subject's status with regard to the primary outcome. Each reviewer will be asked to define each secondary outcome as present or absent, without knowledge of the other reviewers' determinations. In the event of a disagreement between the first and second reviewer, the determination of a third reviewer will be used to define the outcome. No reviewer will be made aware of their designation as the first, second or third reviewer.

Acute Kidney injury will be reported using defined using the Acute Kidney Injury Network (AKIN) definitions (stages 1-3).⁹⁰ KDIGO guidelines do recommends a more standard definition of AKI than for CIN.³⁸ While we do agree with this recommendation, in principle, we are planning a study aimed at changing imaging practices of physicians in specialties that are not as familiar with the. We do plan to measure and report AKIN 1-3 outcomes. We also plan the enrollment of a heterogeneous cohort of patients with renal function ranging from normal to significantly impaired and patients with a range of acute and chronic illnesses of varying severity, consistent with patients treated in the emergency care setting.

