Sample Size We will use a prospective validation study design for the previously derived decision rule (AKIrisk Score), classifying subjects into low AKI-risk group. We will recruit 100 subjects undergoing CTPA with an AKIrisk Score <2 . Since the overall AKI rate in our patient population of interest is $<10\%$ (see *Preliminary Data*), the group of subjects with AKIrisk Score <2 will have much lower AKI rate. Assuming 5% AKI rate in this low risk group, the upper limit of one way 95% confidence interval will be $\leq 9.3\%$ with a sample size of 100 (adjusted for dropout and screening failures).

Secondary Outcome Analysis: We will measure several secondary outcomes of which almost all are dichotomous (e.g. death, renal failure, stroke and/or other acute arterial vascular events). We will use a logistic regression model including the baseline covariates in the model. In case of rare events, we will use an exact logistic regression analysis. For the change in continuous outcomes, we will use ANCOVA model including the baseline covariates. Using similar analyses, we will compare baseline outcomes between enrolled subjects and subjects who will meet the inclusion criteria but decline participation in the study. Finally, we will compare outcomes of patients, relative to the AKIrisk Score, and we will compare outcomes and demographic data of those who enroll versus those who meet inclusion but decline participation to assess for possible bias induced by the informed consent process.⁸⁴

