4.2 Inclusion Criteria

1. Age ≥ 18 years
2. CTPA ordered by the treating provider to evaluate PE.
3. Pre-test probability of PE $\leq 20\%$ (defined using the PE Pretest Consult Score)
4. For randomization to CTPA or VQ imaging: Pre-imaging CIN risk $\geq 20\%$ (AKIrisk Score ≥ 2 points)

- A lower-risk subset of 100 patients (AKIrisk Score <2) will be enrolled and followed. These patients will complete the CTPA as ordered by their provider (not randomized). Data from this lower-risk subset, along with high-risk patients randomized to CTPA will be used will be used to validate the AKIrisk Score, alone and in combination with NGAL and eGFR_{CYS} (Study Aims 1 and 3).

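### The hypothesis says the AKIrisk Score is more accurate than creatinine screening, but no planned analysis uses creatinine as comparator, and sampling by score makes the planned accuracy figures unfit for comparison with the preliminary ones

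*Combined protocol and SAP*

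**What the plan says.** The first half of the hypothesis (Section 1.2) is comparative: "a clinical decision rule more accurately risk-stratifies patients for AKI than creatinine screening". The places where an analysis of it could be expected contain the following.

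- **Section 1.2, specific aims.** Aim 1 tests whether a score below 2 predicts a risk under 10%. Aim 2 reads "Test if the use of acute-phase markers of renal dysfunction, Cystatin-C and/or NGAL, improves the predictive accuracy of the AKIrisk Score". Aim 3 is the randomized comparison of CTPA with VQ.
- **Section 2.1, Primary Outcome Analysis.** Two validation steps: "Measure the AKI rate in the low-risk group (AKIRisk Score <2) with a desired margin of error", and "Compute sensitivity and specificity of the decision rule".
- **Section 2.2.** The first secondary objective concerns the score alone or with Cystatin-C or NGAL. The secondary analysis adds only that "we will compare outcomes of patients, relative to the AKIrisk Score".
- **Section 4.2.** The validation set is defined by "Data from this lower-risk subset, along with high-risk patients randomized to CTPA will be used", for the score alone or combined with NGAL and Cystatin-C eGFR.

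Section 5.1 collects a baseline creatinine. Its stated use is as the baseline from which the primary outcome is defined.

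**The concern.** A hypothesis that names a comparator needs an analysis containing that comparator. Here there is none, so the trial as planned can neither support nor refute the first half of its hypothesis.

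Two consequences follow. The claim would continue to rest on preliminary data from the cohort that produced the score, although Section 1.2 itself argues that practice will change only after prospective validation. The trial will also report a sensitivity and specificity for the score. With no creatinine result from the same patients, the natural yardstick is the preliminary creatinine result in Section 1.5. Because enrolment depends on the score, that would be an invalid comparison.

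**Working it through.** **1. The plan's own validation figure.** Section 2.2 assumes 5% AKI in the score <2 group and gives a one-sided 95% upper limit of 9.3% with 100 patients, adjusted for dropout. With 30% dropout, n = 70, and 0.05 + 1.645 × √(0.05 × 0.95 / 70) = 0.0928. The figure reproduces. It concerns an absolute rate in one group and does not bear on score versus creatinine. No sample size, test or precision is stated for that comparison.

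**2. What the preliminary data say (Section 1.5 and Table 2).**

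| Test | Sensitivity | Specificity | AUROC (95% CI) | Sens + spec − 1 |
|---|---|---|---|---|
| AKIrisk Score ≥2 | 56% | 81% | 0.74 (0.68 to 0.81) | 0.37 |
| eGFR ≤60 | 13% | 87% | 0.55 (0.47 to 0.63) | 0.00 |

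Both rows come from the same emergency CT cohort. The score was built there after evaluating more than 100 candidate factors at varying thresholds, whereas eGFR was applied at a fixed cut-off. Optimism from derivation therefore favours the score.

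**3. The population implied by those figures.** With PPV 27%, sensitivity 56% and specificity 81%:

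- AKI prevalence = 0.27 × 0.19 / (0.56 × 0.73 + 0.27 × 0.19) = 0.0513 / 0.4601 = 11.1%
- share with score ≥2 = 0.56 × 0.1115 / 0.27 = 23.1%
- AKI risk with score <2 = 0.44 × 0.1115 / 0.769 = 6.4%

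**4. What the trial would show if the score performed exactly as before.** Section 1.6 gives 300 CTPA patients at score ≥2 and 100 below. Assume 30% dropout in both groups, leaving 210 and 70 evaluable.

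- AKI events: 210 × 0.27 = 56.7 and 70 × 0.064 = 4.5, total about 61
- unweighted sensitivity = 56.7 / 61.2 = 93%
- unweighted specificity = 70 × 0.936 / (70 × 0.936 + 210 × 0.73) = 65.5 / 218.8 = 30%

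The sample has 75% of patients at score ≥2 (210/280), against 23.1% in the implied population. Over AKI rates of 20 to 27% (score ≥2) and 5 to 10% (score <2), unweighted sensitivity is 86 to 94% and specificity 27 to 30%. Reweighting to 23.1%/76.9% returns 56% and 81%.

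The Précis, unlike Section 4.2, describes validation in the VQ arm as well. With both arms, and the same AKI risk assumed in each, the figures would be 113.4 / (113.4 + 4.5) = 96% and 65.5 / (65.5 + 306.6) = 18%.

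**5. Precision of a paired comparison.** Simulations with 210 and 70 patients, weighted to 23.1%/76.9%, used assumed score distributions with AUROC near 0.74 to 0.76 and eGFR with AUROC near 0.55. The standard error of the AUROC difference was about 0.09 to 0.10 if score and eGFR are independent, falling to about 0.07 at an assumed correlation of 0.5. For a true difference of 0.19, power ≈ Φ(0.19/SE − 1.96):

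- SE 0.10: Φ(−0.06) = 48%, 95% half-width 0.20
- SE 0.07: Φ(0.75) = 77%, 95% half-width 0.14

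Precision is limited because the 4 to 5 AKI events expected below score 2 stand for 44% of all AKI cases after weighting.

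**The case against.** The strongest reply is that the clause is a premise. It is introduced concessively, Section 1.1 already asserts the improvement, the alternative hypothesis does not deny it, and none of the three aims tests it. That reading is possible and makes rewording a legitimate remedy. It does not remove the mismatch, because the text presents the clause as hypothesis and its only support is derivation data.

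A second reply is that no section proposes setting the trial's score accuracy beside the preliminary creatinine figures. That is correct; the risk lies in the absence of any other comparator.

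Some stronger readings are tempting, but the documents do not support them:

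- *The claim rests on a single old sensitivity figure.* It does not. Table 2 also gives specificity and AUROC for eGFR, and Section 1.5 gives the same measures for the score. The AUROC gap is 0.19, about 0.09 to 0.29 if the two estimates are treated as independent.
- *Creatinine would do far better in this trial, because median eGFR is 37 in Table 3.* Table 3 consists of patients sent for VQ and CTPA controls matched to them on eGFR, so the 37 reflects selection and matching. A higher positivity rate in an uninformative test also lowers its specificity by as much as it raises sensitivity, so sensitivity + specificity − 1 stays at 0.
- *Section 1.2 promises evidence on creatinine screening.* It refers only to unnecessary screening and prevention practices in general, and the randomized comparison could inform those whichever predictor is better.

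The unlisted baseline covariates in the logistic models do not fill the gap, since adjustment does not compare predictive accuracy.

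**Conclusion.** The point holds in this form: one half of the stated hypothesis has no planned analysis, and the accuracy figures that are planned cannot substitute for it. Sampling by score alone would move a true 56%/81% to about 93%/30%. That size rests on the preliminary PPV, sensitivity and specificity, on 30% dropout in both score groups, and on validation in CTPA patients as in Section 4.2. The direction and approximate size hold across the ranges shown.

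A reader might infer that the score is no better than creatinine, or that the trial's main result is compromised. Neither follows. The preliminary data favour the score, though probably with optimism, and the comparison of CTPA with VQ does not depend on this point. The plan should be changed, but the defect is confined to the prediction part of the study.

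**What to change.** Add to Sections 2.1 and 2.2, for CTPA patients with a baseline creatinine:

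- Compare the AKIrisk Score with creatinine-based eGFR (continuous and at the ≤60 cut-off) for the primary AKI outcome in the same patients. Report differences in AUROC, sensitivity and specificity with 95% confidence intervals from a bootstrap resampled within score group.
- Weight both tests by the fractions with score <2 and ≥2 recorded at eligibility screening. Repeat with the preliminary 23%/77% split as a stated sensitivity assumption.
- Report the score's own sensitivity and specificity with the same weights.
- State the expected precision, with its range, and that any claim of superiority over creatinine will rest only on this comparison.

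Alternatively, reword the clause in Section 1.2 as background and make no superiority claim from the trial.

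The cost is SAP wording and one analysis, with no extra patients, visits or assays. The one operational addition is a screening log of scores. Section 4.1 describes completing the score at screening, sometimes with a bedside dipstick, but does not commit to recording the fractions. The main drawback is that the comparison may be inconclusive, with power of roughly one half to three quarters at the preliminary values.
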